6.7 BASELINE, TIME WINDOWS AND CALCULATED VISITS

6.7.1 Baseline

If not otherwise stated, baseline is defined as the last measurement prior to first drug administration.

ECG interval data:

CTP Section 7.1: Throughout the study protocol, the term "baseline" (if not specified further) refers to the 3 pre-dose triplicate ECG measurements at Visits 2-6 (i.e. a separate baseline for each period will be derived from the 9 ECG recordings that comprise 4 cardiac cycles each).

The mean of the values calculated for the 3 pre-dose time points per period is also denoted as 'period baseline'. 'Change from baseline' always refers to the period baseline. An additional 'subject baseline' is defined as the arithmetic mean of the period baselines per subject and will only be used in the context of MMRM analyses; for further details see Section 7.4.

6.7.2 Time windows

Time windows are defined in Section 6.1 of the CTP.

Adherence to time windows will be checked at the RPM.

The following tables summarize the time points of interval extractions from the 12-lead Holter recordings as well as the planned time intervals for Holter evaluations with regard to cardiac arrhythmia events.

TSAP for BI Trial No: 1289-0038 Page 22 of 44

Proprietary confidential information © 2019 Boehringer Ingelheim International GmbH or one or more of its affiliated companies

Table 6.7.2: 2 Time schedule for extractions of triplicate ECGs from Holter recording during treatment periods

	Planned times [hh:mm] relative to administration of study drug				
Visit	Pre-dose	On treatment			
2-6	-0:50, -0:35, -0:20	0:20, 0:40, 1:00, 1:30, 2:00, 2:30, 3:00, 4:00, 8:00, 12:00, 24:00			

TSAP for BI Trial No: 1289-0038 Page 23 of 44

Proprietary confidential information © 2019 Boehringer Ingelheim International GmbH or one or more of its affiliated companies

Proprietary confidential information © 2019 Boehringer Ingelheim International GmbH or one or more of its affiliated companies

7. PLANNED ANALYSIS

For End-Of-Text (EoT) tables, the set of summary statistics is: N / Mean / SD / Min / Q1 (lower quartile) / Median / Q3 (upper quartile) / Max.

For tables that are provided for endpoints with some extreme data, median, quartiles and percentiles should be preferred to mean, standard deviation, minimum and maximum.

Tabulations of frequencies for categorical data will include all possible categories and will display the number of observations in a category as well as the percentage (%) relative to the respective treatment group (unless otherwise specified, all subjects in the respective subject set whether they have non-missing values or not).

The precision for percentages should be one decimal point. The category missing will be displayed only if there are actually missing values.

7.1 DEMOGRAPHIC AND OTHER BASELINE CHARACTERISTICS

Only descriptive statistics are planned for this section of the report.

7.2 CONCOMITANT DISEASES AND MEDICATION

Only descriptive statistics are planned for this section of the report.

7.3 TREATMENT COMPLIANCE

Only descriptive statistics are planned for this section of the report.

7.4 PRIMARY ENDPOINT(S)

7.4.1 Primary analysis of the primary endpoint(s)

CTP Section 7.1.3: For the analysis of the QTcF changes from baseline at each time point between 20 min to 24 hours after dosing, a linear mixed-effects model for repeated measurements (MMRM) will be used. The analyses will be based on the ECG set.

The comparison between each dose of BI 409306 and placebo will be performed pairwise, i.e. data not relevant for the comparison of interest will be excluded. Data from both placebo periods per subject will be included simultaneously in the analysis, using the same treatment code 'placebo' but differentiated by the respective period numbers. This means that the model defined below can directly be used for estimating the treatment contrast between the active drug under consideration and placebo, using the observations from both placebo periods. In the following, the 'subject baseline' is defined as the arithmetic mean of the period baselines per subject (only from the periods involved in the comparison, i.e. the period baseline of the active treatment period and those of the 2 placebo periods).

The MMRM is based on Schall and Ring $(\underline{14})$ and includes the fixed categorical effects of 'treatment', 'period' and 'time', the 'treatment-by-time' interaction and 'period-by-time'

Proprietary confidential information © 2019 Boehringer Ingelheim International GmbH or one or more of its affiliated companies

interactions, as well as the continuous fixed covariates 'period baseline' and 'subject baseline', and the 'period baseline-by-time' interaction and 'subject baseline-by-time' interaction. Subject is included as a random effect on the intercept. For the repeated effect 'time', an unstructured covariance pattern is chosen, using the blocking factor 'subject-by-period'. Note that the 'subject baseline' is included in the model to avoid cross-level bias affecting treatment comparisons; see Kenward and Roger (13).

More precisely, the model is given by

$$Y_{ikm(j)} = \mu + \gamma B_{im} + \gamma' \bar{B}_i + \pi_m + \tau_j + \zeta_k + \gamma_k B_{im} + \gamma'_k \bar{B}_i + (\pi \zeta)_{mk} + (\tau \zeta)_{jk} + s_i + e_{ikm},$$

$$s_i \sim N(0, \sigma_s^2), (e_{i1m}, ..., e_{iKm}) \sim N_K(\mathbf{0}, \Psi),$$

where i=1,...,I indicates the subject, k=1,...,K the time point within period, m=1,...,M the period and j=1,2 the treatment,

 $Y_{ikm(j)}$ the QTcF change from period baseline for subject *i* receiving treatment *j* in period *m* at repeated measures time point *k*,

 μ the overall intercept,

 B_{im} the baseline value for subject *i* in period *m* (period baseline),

γ the associated covariate effect of period baseline,

 \bar{B}_i the subject baseline value (mean of 3 period baselines) for subject i,

 γ' the associated covariate effect of subject baseline,

 π_m the effect of period m,

 τ_i the effect of treatment j,

 ζ_k the effect of time k,

 γ_k the interaction effect of period baseline and time,

 γ'_k the interaction effect of subject baseline and time,

 $(\pi\zeta)_{mk}$ the interaction effect of period and time,

 $(\tau\zeta)_{ik}$ the interaction effect of treatment and time,

 s_i the random effect of subject i on intercept, assumed mutually independent across subject,

 e_{ikm} the random error associated with subject i for time k and period m, assumed

Proprietary confidential information © 2019 Boehringer Ingelheim International GmbH or one or more of its affiliated companies

independent across period and subject (indices m, i), and

 Ψ an unstructured K-by-K covariance matrix.

The random subject effects s_i and the random errors e_{ikm} are assumed to be independent of one another.

CTP Section 7.3.1: For the pairwise comparisons between each dose of BI 409306 and placebo, mean treatment differences in the QTcF changes from baseline at each time point will be estimated by the differences in the corresponding least-squares means. Two-sided 90% confidence intervals based on the t-distribution will also be computed for each time point. The null hypothesis will be rejected if the maximum upper confidence limit for the mean difference in the QTcF changes from baseline between BI 409306 and placebo is less than 10 msec.

Proprietary confidential information © 2019 Boehringer Ingelheim International GmbH or one or more of its affiliated companies

7.5 SECONDARY ENDPOINT(S)

7.5.1 Key secondary endpoint(s)

This section is not applicable as no key secondary endpoint has been specified in the protocol.

7.5.2 (Other) Secondary endpoint(s)

7.5.2.1 Assessment of assay sensitivity

CTP Section 7.3.2.1: The effect of moxifloxacin on the QTcF changes from baseline in comparison with placebo will be assessed using the same MMRM as applied in the primary analysis.

For this analysis, only the data from the moxifloxacin and placebo periods will be used.

For describing the time course of the effect of moxifloxacin on QTcF, 90% confidence intervals for the mean differences of the QTcF changes from baseline between moxifloxacin and placebo will be provided.

For the formal test of assay sensitivity at level $\alpha=5\%$, the method by Hochberg (10) will be applied. To this end, the three single hypotheses that the mean difference in the QTcF change from baseline between moxifloxacin and placebo is less than or equal to 5 msec at a given time point (out of the three time points 2, 3, and 4 hours after drug administration) will be tested based on the results of the MMRM (fitted to the data for all time points). If the largest of the three p-values is less than 5% (= α), then all single hypotheses can be rejected. If the second largest p-value is less than 2.5% (= α /2), then the corresponding null hypothesis and the one regarding the test with the lowest p-value can be rejected. If the lowest p-value is less than 1.667% (= α /3), then only the null hypothesis corresponding to this p-value can be rejected. Note that it is sufficient to reject only one of the three single null hypotheses in order to reject the overall null hypothesis stated in CTP Section 7.2 (i.e., the intersection of the three single hypotheses), and hence to show assay sensitivity.

7.5.2.2 Analyses of the heart rate

For each dose of BI 409306, the HR changes from baseline at each time point between 20 min to 24 hours after dosing will be analysed by applying the same model as in the primary analyses and calculating the corresponding 90 % CIs for the mean difference between BI 409306 and placebo. For these analyses, only the HR data from the respective BI 409306 dose and placebo will be used.

TSAP for BI Trial No: 1289-0038 Page 28 of 44

Proprietary confidential information © 2019 Boehringer Ingelheim International GmbH or one or more of its affiliated companies

TSAP for BI Trial No: 1289-0038 Page 29 of 44

Proprietary confidential information © 2019 Boehringer Ingelheim International GmbH or one or more of its affiliated companies

TSAP for BI Trial No: 1289-0038 Page 30 of 44

Proprietary confidential information © 2019 Boehringer Ingelheim International GmbH or one or more of its affiliated companies

TSAP for BI Trial No: 1289-0038 Page 31 of 44

Proprietary confidential information © 2019 Boehringer Ingelheim International GmbH or one or more of its affiliated companies

Proprietary confidential information © 2019 Boehringer Ingelheim International GmbH or one or more of its affiliated companies

7.7 EXTENT OF EXPOSURE

Descriptive statistics are planned for this section of the report based on the TS. The date and time of drug administration will be listed for each subject.

7.8 SAFETY ANALYSIS

CTP Section 7.3: *The TS will be used for all other safety summaries and all safety listings.*

7.8.1 Adverse events

AEs will be coded with the most recent version of MedDRA.

Unless otherwise specified, the analyses of adverse events will be descriptive in nature. All analyses of AEs will be based on the number of subjects with AEs and NOT on the number of AEs.

For analysis multiple AE occurrence data on the eCRF will be collapsed into an AE provided that all of the following applies:

- All AE attributes are identical (lower level term, intensity, action taken, therapy required, seriousness, reason for seriousness, relationship, outcome, AE of special interest).
- The occurrences were time-overlapping or time-adjacent (time-adjacency of 2 occurrences is given if the second occurrence started at most 1 hour after the first occurrence ended).

For further details on summarization of AE data, please refer to "Analysis and Presentation of Adverse Event Data from Clinical Trials" (5) and "Handling of missing and incomplete AE dates" (3).

Proprietary confidential information © 2019 Boehringer Ingelheim International GmbH or one or more of its affiliated companies

The analysis of AEs will be based on the concept of treatment emergent AEs. That means that all AEs will be assigned to screening, on-treatment or follow-up phases as defined in Section 6.1. AEs will be analysed based on actual treatments, as defined in Table 6.1: 1.

In addition to the presentation of AEs in separate study periods, both the events in the two placebo periods, and the events of the two periods of (the different doses of) BI 409306 (see Section 6.1) will be added. The interpretation of this summary for "Total BI" is "events following a dose of at least the therapeutic dose level". When comparing "Total Pbo" and "Total BI", "time under risk" is similar.

An overall summary of AEs will be presented. This overall summary will comprise summary statistics for the class of other significant AEs according to ICH E3 (6) and for the class of AESIs.

CTP Section 5.2.2.1: *The following is considered as AESI:*

Hepatic injury

A hepatic injury is defined by the following alterations of hepatic laboratory parameters:

- o an elevation of AST (aspartate transaminase) and/or ALT (alanine transaminase) ≥3-fold ULN combined with an elevation of total bilirubin ≥2-fold ULN measured in the same blood sample, or
- o aminotransferase (ALT, and/or AST) elevations \geq 10 fold ULN

According to ICH E3 (6), AEs classified as 'other significant' needs to be reported and will include those non-serious and non-significant adverse events with

- (i) 'action taken = discontinuation' or 'action taken = reduced', or
- (ii) marked haematological and other lab abnormalities or lead to significant concomitant therapy as identified by the Clinical Monitor/Investigator at a Medical Quality Review Meeting.

The frequency of subjects with adverse events will be summarised by treatment, primary system organ class and preferred term. Separate tables will be provided for subjects with other significant adverse events according to ICH E3 (6), for subjects with AESIs and for subjects with serious adverse events. The frequency of subjects with AEs and the frequency of subjects with AEs considered by the investigator to be drug related will also be summarised by maximum intensity, primary SOC and preferred term.

The SOCs and preferred terms within SOCs will be sorted by descending frequency over all treatment groups.

For disclosure of AE data on ClinicalTrials.gov, the frequency of subjects with non-serious AEs occurring with an incidence of greater than 5 % (in preferred terms) will be summarised by treatment, primary SOC and preferred term. The frequency of subjects with SAEs will also be summarised.

For disclosure of AE data in the EudraCT register, the frequency of AEs, the frequency of non-serious AEs with an incidence of greater than 5 % (in preferred terms) and the frequency of SAEs will be summarized.

Proprietary confidential information © 2019 Boehringer Ingelheim International GmbH or one or more of its affiliated companies

For support of lay summaries, the frequency of subjects with drug-related SAEs will be summarized by treatment, primary SOC and preferred term.

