### **7.3.3 Safety analyses**

Adverse events will be coded using the Medical Dictionary for Drug Regulatory Activities (MedDRA). Standard BI summary tables and listings will be produced. All adverse events with an onset between start of treatment and end of the REP, a period of 24 hours after the last dose of trial medication (in treatment periods with BI drug or placebo) or a period of 4 days after the last dose of trial medication (in moxifloxacin treatment period), will be assigned to the on-treatment period for evaluation. The safety analysis will be done by ‘treatment at onset’.

All treated subjects will be included in the safety analysis. In general, safety analyses will be descriptive in nature and will be based on BI standards.

Statistical analysis and reporting of adverse events will concentrate on treatment-emergent adverse events, i.e. all adverse events occurring between start of treatment and end of the REP. Adverse events that start before first drug intake and deteriorate under treatment will also be considered as ‘treatment-emergent’.

Frequency, severity, and causal relationship of adverse events will be tabulated by system organ class and preferred term after coding according to the current version of the Medical Dictionary for Drug Regulatory Activities (MedDRA) at database lock.

Laboratory data will be listed only. Values outside the reference range as well as values defined as clinically relevant will be flagged.

Vital signs, physical examinations, or other safety-relevant data observed at screening, baseline, during the course of the trial and at the end-of-trial evaluation will be assessed with regard to possible changes compared to findings before start of treatment.

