6. GENERAL ANALYSIS DEFINITIONS

6.1 TREATMENTS

For basic information on treatments to be administered and assignment of treatment groups, refer to Section 4 of the CTP.

For the statistical analysis of AEs, the following analysis phases specified in Table 6.1: 1 will be defined for each subject.

Table 6.1: 1 Analysis phases for statistical analysis of AEs

Study analysis phase	Label	Start	End
Screening	Screening	Date of informed consent	Date/time of first administration of study drug in period 1
On-treatment	Placebo 1, Placebo 2, BI 50 mg, BI 250 mg, or Mox 400 mg, respectively	Date/time of administration of study drug	Date/time of administration of study drug + residual effect period or Date/time of administration of study drug in the next treatment period or 12:00 a.m. on day after subject's end of study participation date, whatever comes first
Follow-up	FUP Placebo 1, FUP Placebo 2, FUP BI 50 mg, FUP BI 250 mg, or FUP Mox 400 mg, respectively	End of the respective ontreatment period (see line above)	Date/time of administration of study drug in the next treatment period, if applicable, otherwise 12:00 a.m. on day after subject's end of study participation date

CTP Section 1.2.4: The Residual Effect Period (REP) of BI 409306 is 24 hours. The REP of moxifloxacin is 4 days.

For Placebo, the REP is set to 24 hours, i.e. equal to that of BI 409306.

In CTR Section 15 and Appendix 16.1.13.1.8, AE displays will present results for the ontreatment phase only.

TSAP for BI Trial No: 1289-0038 Proprietary confidential information © 2019 Boehringer Ingelheim International GmbH or one or more of its affiliated companies

In CTR Section 15 AE tables (but not in Appendix 16.1.13.1.8 AE tables), the following totals will be provided in addition:

- "Total Pbo", defined as the total over all on-treatment phases involving treatment with placebo
- "Total BI", defined as the total over all on-treatment phases involving treatment with BI 409306
- "Total", defined as the total over all on-treatment phases

The treatments will be presented in Section 15 AE tables in the following sort order: Placebo 1, Placebo 2, BI 50 mg, BI 250 mg, Mox 400 mg, Total Pbo, Total BI, Total.

Statistical analyses of vital signs will be conducted by treatment (Placebo 1, Placebo 2, BI 50 mg, BI 250 mg, Mox 400 mg), with clear differentiation between baseline (see Section 6.7) and on-treatment measurements.

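### SAP 7.8.1 can merge an AE that starts after dosing with an identical complaint that began before the dose, which may drop it from the on-treatment AE tables

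*SAP*

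**What the plan says.** SAP 7.8.1 introduces the rule with "For analysis multiple AE occurrence data on the eCRF will be collapsed into an AE provided that all of the following applies" and then lists two conditions.

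- Attributes: "All AE attributes are identical (lower level term, intensity, action taken, therapy required, seriousness, reason for seriousness, relationship, outcome, AE of special interest". Treatment, period and analysis phase are not in the list.
- Time: the occurrences overlap or are adjacent, and "time-adjacency of 2 occurrences is given if the second occurrence started at most 1 hour after the first occurrence ended". Dosing time is not mentioned.

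The same section then places AEs in phases: "That means that all AEs will be assigned to screening, on-treatment or follow-up phases as defined in" SAP 6.1. In Table 6.1: 1 of the SAP the on-treatment phase starts at "Date/time of administration of study drug". Before that point the subject is in Screening (period 1) or in the follow-up phase of the previous treatment. For CTR Section 15 and Appendix 16.1.13.1.8, SAP 6.1 says that "AE displays will present results for the ontreatment phase only".

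Protocol 7.3.3 assigns to the on-treatment period "All adverse events with an onset between start of treatment and end of the REP" and attributes events to the treatment at onset. It has one provision for events that begin earlier: those that start before the first drug intake and get worse under treatment also count as treatment-emergent.

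**The concern.** The collapsing rule can join records on either side of a dose, while the phase rule depends on which side of the dose the onset falls. A subject with a mild headache that clears shortly before dosing, and an identical one soon after it, could be recorded as having a single pre-dose headache. The post-dose complaint would then not appear under the treatment just given.

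Under the planned schedule the effect has one direction, because the time just before a dose is never on-treatment. A merge across a dose can take an on-treatment event away but cannot add one. What is at stake is the completeness of the on-treatment AE tables soon after dosing, for BI 409306, moxifloxacin and placebo alike.

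**Working it through.** The plan gives no figure to reproduce. The check applies the SAP's conditions to example records.

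**Inputs**
- Collapsing conditions: SAP 7.8.1.
- Phase boundaries: SAP Table 6.1: 1.
- Residual effect period: 24 hours for BI 409306 and placebo, 4 days for moxifloxacin (SAP 6.1).
- Washout: at least 6 days (protocol 3.1).
- Planned size: 45 subjects and 5 periods; no more than 50 subjects dosed (protocol 3.1 and 3.3.5).
- Assumption A: a merged AE takes the earliest onset among its occurrences.
- Assumption B: collapsing comes before phase assignment. The SAP assigns AEs, not occurrences, to phases, which suggests this order without stating it.

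**Step 1. Phase just before a dose.** The previous on-treatment phase ended at least 6 − 1 = 5 days earlier (BI 409306 or placebo) or 6 − 4 = 2 days earlier (moxifloxacin). The pre-dose time is therefore Screening or follow-up.

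**Step 2. Examples, dose at 08:00.** The gap is the start of the second occurrence minus the end of the first; adjacency needs a gap of 60 minutes or less. Attributes are identical except in row 3. The last two columns count on-treatment AEs under the current rule and under the condition proposed below.

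| Case | First | Second | Gap | Merged now? | Current | With condition |
|---|---|---|---|---|---|---|
| 1 | 06:30–07:40 | 08:30–10:00 | 50 min | yes | 0 | 1 |
| 2 | 06:00–07:20 | 08:30–10:00 | 70 min | no | 1 | 1 |
| 3, second more intense | 06:30–07:40 | 08:30–10:00 | 50 min | no | 1 | 1 |
| 4 | 06:45–08:10 | 08:50–10:00 | 40 min | yes | 0 | 1 |
| 5, overlapping | 06:45–09:00 | 08:30–10:00 | none | yes | 0 | 0 |

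Cases 1 and 4 show the problem. If the first occurrence ended before the dose (case 1), the second must start within 1 hour after it. If the first ran past the dose (case 4), that limit does not apply.

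**Step 3. Can the deterioration provision recover the event?** No. Merging requires equal intensity, so a merged event has not worsened in intensity. The provision also refers only to the first drug intake, so it does not cover periods 2 to 5.

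**Step 4. Size.** The situation could arise at 45 × 5 = 225 planned dosings (50 × 5 = 250 if 50 subjects were dosed and all completed). The tables count subjects, so one merged event changes a cell by at most 1/45 = 2.2 percentage points, and by nothing if the subject has another on-treatment event in that cell. For a term at the edge of the 5% disclosure cut-off in SAP 7.8.1, one subject decides: 3/45 = 6.7% against 2/45 = 4.4%.

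**The case against.** The strongest reply is that the gap may not exist in practice. SAP 7.8.1 refers on to internal reference documents for AE summaries, SAP 6.1 to an Analysis Data Set Plan and SAP 3 to AE macros. A treatment-boundary condition could sit in any of them. Assumptions A and B are also inferences: assigning each occurrence to a phase before collapsing would remove the problem. This stands as a limit on certainty. The SAP's own list, however, reads as complete and contains no such condition.

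Second, a reader might infer that the SAP plainly contradicts protocol 7.3.3. The documents do not support that. The protocol assigns adverse events, not eCRF occurrences, and where one episode ends is a convention. Before the first dose in particular, a complaint that returns unchanged within an hour can fairly be seen as a pre-existing event that did not worsen. What remains is that two separate occurrences, the later with its own post-dose onset, can be reported as one pre-dose event.

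Third, the attribute condition already protects the events that matter most. A change in intensity, relationship, action taken, therapy or outcome blocks the merge. A post-dose event rated drug-related will not be absorbed by an unrelated pre-dose one. In periods 2 to 5 the earlier occurrence could itself be rated related to the previous treatment, but that should be unusual so long after the dose. This stands: the loss is mainly of non-worsening recurrences with the same causality rating.

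Fourth, a blanket ban on merging across a dose would split records such as case 5, which describe one continuous event that began before the dose. This also stands, and the fix is limited accordingly.

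**Conclusion.** The point holds as a minor gap in the SAP text. Read literally, and on assumptions A and B, the rule lets a complaint that began before the dose absorb an identical, non-overlapping one that starts after it, and the later one then drops out of the on-treatment tables. Each case costs at most 1 of 45 subjects (2.2 points) in a cell. The number of cases should be small and cannot be estimated from the documents.

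Three stronger readings are not supported:

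- That several cases per treatment will understate an AE term or move it across the 5% cut-off. The documents give no basis for any such count; the cut-off matters only for a term that happens to sit on it.
- That the trial's cardiac conclusions are touched because the merge acts soon after dosing, when protocol 7.6 expects the largest QTc effect. QTcF and heart rate come from Holter extractions analysed by the MMRM, and AE collapsing does not enter them.
- That the event vanishes from the report. Protocol 7.3.3 also plans AE listings, where the record should still be found.

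**What to change.** Add to the time-adjacency condition in SAP 7.8.1: non-overlapping occurrences are not collapsed if a study drug administration lies between their onsets; the later one is assigned to an analysis phase by its own onset. Overlapping records with identical attributes that form one continuous event starting before the dose may still be collapsed. It would help to state in the same place that a collapsed AE takes the earliest onset. If an internal standard already contains such a condition, the SAP should say so.

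The cost is one sentence and one condition in the AE program. No new data are needed: AE onset and end times are recorded (protocol 5.2.2.2), and dosing date and time are listed per subject (SAP 7.7). The downside is that a few recurrences of pre-dose complaints that did not worsen will be counted as on-treatment AEs. The same condition would apply to every treatment, including placebo.
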